## 6. Final Power Assessment

Date conducted: 12/22/2020

- Re-calculate power in the appropriate excel table, using the revised number of matched patients from the PS-match in Section 9. All other parameters in the table should be the same as in Section 8.

Superiority Analysis (Pooled)	
Number of patients matched	
Reference	3,033
Exposed	3,033
Risk per 1,000 patients	215.25
Desired HR from RCT	0.8
Alpha (2-sided)	0.05
Number of events expected	1305.7065
Power	0.980850168

Superiority Analysis (Optum)	
Number of patients matched	
Reference	1,279
Exposed	1,279
Risk per 1,000 patients	206.60
Desired HR from RCT	0.8
Alpha (2-sided)	0.05
Number of events expected	528.4828
Power	0.727390963

Superiority Analysis ( Marketscan )	
Number of patients matched	
Reference	748
Exposed	748
Risk per 1,000 patients	160.30
Desired HR from RCT	0.8
Alpha (2-sided)	0.05
Number of events expected	239.8088
Power	0.408308308

Superiority Analysis (Medicare)	
Number of patients matched	
Reference	1,006
Exposed	1,006
Risk per 1,000 patients	248.30
Desired HR from RCT	0.8
Alpha (2-sided)	0.05
Number of events expected	499.5796
Power	0.703266933

- Stop analyses until balance and final power assessment are reviewed by primary investigators, FDA, and assigned members of advisory board.

Reviewed by PI:	[name]	Date reviewed:	12/26/20
Reviewed by FDA:		Date reviewed:	
Reasons for stopping analysis (if required):			

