Other Medication - Use of COPD/asthma meds ; n (%)	3,139 (18.2%)	549 (22.6%)	0.1094	1,703 (15.9%)	265 (20.6%)	-0.1219	3,142 (17.2%)	358 (21.6%)	-0.1114	6,281 (13.6%)	907 (16.9%)	-0.0919
HU - Bone mineral density; n (%)	348 (2.0%)	56 (2.3%)	-0.0207	99 (0.9%)	17 (1.3%)	-0.0384	364 (2.0%)	31 (1.9%)	0.0072	712 (1.5%)	087 (1.6%)	-0.0081
HU - Flexible Sigmoidoscopy or colonoscopy or CT virtual colonoscopy; n (%)	646 (3.7%)	86 (3.5%)	0.0107	440 (4.1%)	54 (4.2%)	-0.0050	789 (4.3%)	63 (3.8%)	0.0254	1,430 (3.1%)	149 (2.8%)	0.0117
HU - Flu vaccine; n (%)	2,851 (16.5%)	446 (18.4%)	-0.0501	1,106 (10.3%)	142 (11.0%)	-0.0227	4,410 (24.1%)	491 (29.6%)	-0.1243	7,261 (15.7%)	937 (17.4%)	-0.0458
HU - Mammogram; n (%)	775 (4.5%)	135 (5.6%)	-0.0503	404 (3.8%)	62 (4.8%)	-0.0493	830 (4.5%)	88 (5.3%)	-0.0371	1,605 (3.5%)	223 (4.2%)	-0.0364
HU - Fram Score: Empirical Version 365 days												
...mean (sd)	0.23 (0.07)	0.22 (0.06)	0.1534	0.20 (0.06)	0.20 (0.05)	0.0000	0.27 (0.09)	0.24 (0.07)	0.3721	0.24 (0.08)	0.22 (0.06)	0.2280
...median [IQR]	0.21 (0.18, 0.26)	0.21 (0.18, 0.25)	0.0000	0.19 [0.16, 0.23]	0.19 [0.16, 0.21]	0.0000	0.25 [0.20, 0.32]	0.23 [0.19, 0.27]	0.2481	0.22 (0.08)	0.21 (0.06)	0.1414
HU - Number of hospitalizations during CAP												
...mean (sd)	1.06 (0.84)	1.03 (0.76)	0.0375	0.96 (0.74)	0.90 (0.68)	0.0844	1.39 (1.10)	1.04 (0.89)	0.3498	1.17 (0.93)	1.00 (0.78)	0.1981
...median [IQR]	1.00 [1.00, 1.00]	1.00 [1.00, 1.00]	0.0000	1.00 [1.00, 1.00]	1.00 [1.00, 1.00]	0.0000	1.00 [1.00, 2.00]	1.00 [0.00, 1.00]	0.0000	1.00 [0.00, 1.00]	1.00 (0.78)	0.0000
HU - Number of Emergency Department (ED) visits												
...mean (sd)	1.71 (2.73)	1.79 (2.36)	-0.0314	2.23 (4.68)	2.17 (3.64)	0.0143	2.07 (2.66)	1.59 (2.55)	0.1842	1.92 (3.26)	1.82 (2.77)	0.0496
...median [IQR]	1.00 [0.00, 2.00]	1.00 [0.00, 2.00]	0.0000	0.00 [0.00, 3.00]	0.00 [0.00, 3.00]	0.0000	1.00 [0.00, 3.00]	1.00 [0.00, 2.00]	0.0000	0.77 (3.26)	0.76 (2.77)	0.0033
HU - Number of Internal Medicine/Family Medicine Visits												
...mean (sd)	14.57 (17.87)	14.29 (17.89)	0.0157	9.73 (14.69)	9.03 (13.38)	0.0498	12.75 (15.11)	8.88 (11.78)	0.2857	12.73 (16.10)	11.36 (15.17)	0.0876
...median [IQR]	9.00 [4.00, 19.00]	9.00 [4.00, 19.00]	0.0000	5.00 [2.00, 12.00]	5.00 [2.00, 11.00]	0.0000	8.00 [4.00, 16.00]	6.00 [3.00, 11.00]	0.1476	7.68 (16.10)	7.11 (15.17)	0.0364
HU - Number of Distinct Medication Prescriptions (not generalized to generics)												

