Other Medication - Use of antidepressants ; n (%)	306 (23.9%)	317 (24.8%)	-0.0210	159 (21.3%)	159 (21.3%)	0.0000	284 (28.2%)	280 (27.8%)	0.0089	590 (19.5%)	597 (19.7%)	-0.0050
Other Medication - Use of lithium ; n (%)*	0 (0.0%)	0 (0.0%)	#DIV/0!	3 (0.4%)	0 (0.0%)	0.0896	2 (0.2%)	0 (0.0%)	0.0633	002 (0.1%)	000 (0.0%)	0.0447
Other Medication - Use of Benzodiazepine; n (%)	397 (15.4%)	187 (14.6%)	0.0224	92 (12.3%)	104 (13.9%)	-0.0474	131 (13.0%)	141 (14.0%)	-0.0293	328 (10.8%)	328 (10.8%)	0.0000
Other Medication - Use of opioids ; n (%)	385 (30.1%)	386 (30.2%)	-0.0022	213 (28.5%)	206 (27.5%)	0.0223	267 (26.5%)	281 (27.9%)	-0.0315	652 (21.5%)	667 (22.0%)	-0.0121
Other Medication - Use of COPD/asthma meds ; n (%)	296 (23.1%)	269 (21.0%)	0.0507	139 (18.6%)	152 (20.3%)	-0.0430	195 (19.4%)	218 (21.7%)	-0.0569	491 (16.2%)	487 (16.1%)	0.0027
HU - Bone mineral density; n (%)	28 (2.2%)	28 (2.2%)	0.0000	8 (1.1%)	9 (1.2%)	-0.0094	16 (1.6%)	14 (1.4%)	0.0165	044 (1.5%)	042 (1.4%)	0.0084
HU - Flexible Sigmoidoscopy or colonoscopy or CT virtual colonoscopy; n (%)	61 (4.8%)	55 (4.3%)	0.0240	30 (4.0%)	27 (3.6%)	0.0209	36 (3.6%)	41 (4.1%)	-0.0260	097 (3.2%)	096 (3.2%)	0.0000
HU - Flu vaccine; n (%)	235 (18.4%)	238 (18.6%)	-0.0052	76 (10.2%)	83 (11.1%)	-0.0292	306 (30.4%)	304 (30.2%)	0.0044	541 (17.8%)	542 (17.9%)	-0.0262
HU - Mammogram; n (%)	63 (4.9%)	62 (4.8%)	0.0047	36 (4.8%)	30 (4.0%)	0.0390	51 (5.1%)	46 (4.6%)	0.0233	114 (3.8%)	108 (3.6%)	0.0106
HU - Frailty Score: Empirical Version 365 days												
...mean (sd)	0.22 (0.06)	0.22 (0.06)	0.0000	0.20 (0.05)	0.19 (0.05)	0.2000	0.24 (0.07)	0.24 (0.07)	0.0000	0.22 (0.06)	0.22 (0.06)	0.0000
...median (IQR)	0.21 [0.18, 0.25]	0.21 [0.18, 0.25]	0.0000	0.18 [0.16, 0.22]	0.18 [0.16, 0.21]	0.0000	0.22 [0.19, 0.27]	0.22 [0.19, 0.27]	0.0000	0.21 [0.16, 0.26]	0.21 [0.16, 0.26]	0.0000
HU - Number of hospitalizations during CAP												
...mean (sd)	1.06 (0.77)	1.08 (0.76)	-0.0261	0.98 (0.65)	0.95 (0.66)	0.0458	1.07 (0.91)	1.07 (0.90)	0.0000	1.04 (0.79)	1.04 (0.79)	0.0000
...median (IQR)	1.00 [1.00, 1.00]	1.00 [1.00, 1.00]	0.0000	1.00 [1.00, 1.00]	1.00 [1.00, 1.00]	0.0000	1.00 [1.00, 1.00]	1.00 [0.95, 1.00]	0.0000	1.00 [0.97, 1.00]	1.00 [0.97, 1.00]	0.0000
HU - Number of Emergency Department (ED) visits												
...mean (sd)	1.81 (2.51)	1.84 (2.32)	-0.0124	2.56 (5.33)	2.40 (3.90)	0.0343	1.73 (2.19)	1.65 (2.78)	0.0320	1.97 (3.35)	1.92 (2.93)	0.0159

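### Appendix B computes standardized differences from rounded display values, so its after-matching frailty figures (including 0.2000 in MarketScan) show neither balance nor imbalance

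*Protocol*

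**What the plan says.** Section 9 (Balance Assessment) asks for covariate balance after 1:1 propensity score matching and refers to Appendix B for the table. The Final Power Assessment section then sets a hold: "Stop analyses until balance and final power assessment are reviewed by primary investigators, FDA, and assigned members of advisory board". The investigator's review is dated there, the FDA review carries no date, and the field for reasons to stop is empty.

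Appendix B gives mean (SD) by arm and a standardized difference. For the frailty score after matching it prints:

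- Optum: "0.22 (0.06) 0.22 (0.06) 0.0000" (the pooled columns show the same figures)
- MarketScan: "0.20 (0.05) 0.19 (0.05) 0.2000"
- Medicare: "0.24 (0.07) 0.24 (0.07) 0.0000"

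Before matching it prints "0.23 (0.07) 0.22 (0.06) 0.1534" for Optum, "0.20 (0.06) 0.20 (0.05) 0.0000" for MarketScan and "0.27 (0.09) 0.24 (0.07) 0.3721" for Medicare. Frailty is not on the footnoted list of variables left out of the propensity score model. The document gives no balance limit and no comment on the MarketScan value.

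**The concern.** The MarketScan 0.2000 is the largest mean-based standardized difference after matching in the legible rows, and it falls on a covariate that appears to be in the propensity score. It is also exactly 0.01/0.05, one display step divided by the printed SD. That suggests the column was computed from the displayed figures and not from patient data.

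If so, the frailty entries carry almost no information: a printed 0.0000 could hide a real difference, and a printed 0.2000 could come from a trivial one. Frailty is a plausible confounder here. The primary outcome includes all-cause death, and in Medicare the arms differed before matching even after allowing for rounding (range 0.23 to 0.53). Appendix B is the balance evidence that this document offers for the hold before outcome analysis.

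**Working it through.** **Formulas.** Continuous rows: d = (m1 - m2) / sqrt((s1² + s2²)/2). Binary rows: d = (p1 - p2) / sqrt((p1(1 - p1) + p2(1 - p2))/2). All inputs are from Appendix B.

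**Step 1: reproduce the printed frailty values from the rounded figures.**

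- MarketScan after matching: (0.20 - 0.19) / sqrt((0.05² + 0.05²)/2) = 0.01/0.05 = 0.2000. Printed 0.2000.
- Optum before matching: 0.01 / sqrt((0.07² + 0.06²)/2) = 0.01/0.06519 = 0.1534. Printed 0.1534.
- Medicare before matching: 0.03 / sqrt((0.09² + 0.07²)/2) = 0.03/0.08062 = 0.3721. Printed 0.3721.

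Five other after-matching rows also reproduce to four decimals: Optum age 0.0637, Optum hospitalizations -0.0261, MarketScan hospitalizations 0.0458, MarketScan emergency visits 0.0343, MarketScan cardiologist visits -0.0981. One frailty cell does not: pooled before matching is printed as 0.2280, while its displayed values give 0.02 / sqrt((0.08² + 0.06²)/2) = 0.2828.

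**Step 2: test rounded against exact inputs.** Binary rows print the counts, so the two sources can be told apart (after matching):

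| Row | Counts | Printed | From rounded % | From counts |
|---|---|---|---|---|
| MarketScan heparin | 1 vs 0 of 748 | 0.0447 | 0.0447 | 0.0517 |
| Optum implantable defibrillator | 328 vs 303 of 1,279 | 0.0441 | 0.0441 | 0.0454 |
| Optum other dysrhythmias | 735 vs 736 of 1,279 | 0.0000 | 0.0000 | -0.0016 |

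The printed values follow the rounded percentages. The error is small here, at most 0.007.

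**Step 3: what rounding does to frailty.** One display step is 0.01/0.05 = 0.20 SD in MarketScan, 0.01/0.06 = 0.17 in Optum and 0.01/0.07 = 0.14 in Medicare. Each printed mean and SD may be off by up to 0.005. The widest compatible values put the means at opposite rounding limits and the SDs at their minimum:

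| Database | Printed | Calculation of the limit | Compatible range |
|---|---|---|---|
| Optum, after | 0.0000 | 0.01/0.055 | -0.18 to 0.18 |
| MarketScan, after | 0.2000 | 0.02/0.045 | 0.00 to 0.44 |
| Medicare, after | 0.0000 | 0.01/0.065 | -0.15 to 0.15 |
| MarketScan, before | 0.0000 | 0.01 / sqrt((0.055² + 0.045²)/2) | -0.20 to 0.20 |

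With the SDs taken as exact, the after-matching ranges narrow only to ±0.17, 0.00 to 0.40 and ±0.14.

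**Step 4: the pooled entry.** Weighting the printed database means by 1,279, 748 and 1,006 gives 0.2217 (ACE inhibitors) against 0.2192 (sacubitril/valsartan), or 0.00247/0.06 = 0.04. The printed pooled 0.0000 is also a product of rounding.

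**The case against.** A reader might infer from 0.0000 before matching and 0.2000 after it that matching created a frailty imbalance in MarketScan. The document does not support this. The before-matching entry is as coarse as the later one (-0.20 to 0.20), and the two ranges overlap. The opposite inference, that the zeros in Optum and Medicare establish balance, fails for the same reason.

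The best case against the point is that a large imbalance is unlikely. In MarketScan the quartile row reads "0.18 [0.16, 0.22] 0.18 [0.16, 0.21] 0.0000": equal medians and lower quartiles, with upper quartiles one display step apart. In Optum and Medicare the after-matching medians and quartiles agree to two decimals. Related MarketScan covariates are close: dementia 36 vs 36, comorbidity score 0.0239, age -0.0299. The ranges above are worst-case corners. All this stands and makes values near 0.44 improbable, but the quartiles are rounded to the same two decimals and do not settle the mean difference.

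The reviewers may also have seen unrounded values in the separate balance reports linked in Section 9, and with no FDA date the review may still be open. So it cannot be said that the balance decision was wrongly made, only that the table in this document cannot carry it.

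Materiality is limited too. MarketScan supplies 239.8 of 528.5 + 239.8 + 499.6 = 1,267.9 expected matched events, or 19%. Assume a frailty hazard ratio of 1.2 to 1.5 per SD (not in the document). A true gap of 0.20 would then move the MarketScan HR by about 4% (0.20 × ln 1.2 = 0.036) to 8% (0.20 × ln 1.5 = 0.081), and the pooled HR by 19% of that on the log scale, about 0.7% to 1.5%.

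**Conclusion.** The point holds as a defect in the balance evidence. The standardized differences in the rows checked were computed from rounded display values; this is close to harmless except for frailty, where the after-matching entries are uninformative. Compatible worst-case ranges are -0.18 to 0.18 (Optum), 0.00 to 0.44 (MarketScan) and -0.15 to 0.15 (Medicare). Against the conventional limit of 0.1, which is an assumption here, every range includes values on both sides.

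Neither a real imbalance nor a bias in the effect estimate is shown. The conclusion assumes ordinary rounding to two decimals and the standard pooled-SD formula, which the reproduced values support. The true differences cannot be recovered from the document.

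**What to change.** Before the balance hold in the Final Power Assessment section is lifted:

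1. Recompute the standardized differences from unrounded patient-level data, separately for each database. This is essential for frailty; for the rest of the column it comes with the same rerun, and the pooled before-matching frailty cell should be checked at the same time.
2. Print the frailty mean and SD to three or four decimals.
3. State the balance limit in use and comment on the recomputed MarketScan frailty value.
4. Only if that value exceeds the limit, refine the frailty term in the MarketScan propensity score (for example with categories or a spline) and re-match there before any outcome analysis.

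The cost is one rerun of the balance table. A MarketScan re-match, with its matched count and power updated, follows only if step 4 applies.

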### 6.3 Outcome variables and study follow-up:

#### 6.3.1 Outcome variables

Effectiveness outcome variables of interest (definitions provided in **Appendix A**):

- **Primary outcome:** Composite of hospitalization for heart failure and all-cause mortality
- Secondary outcomes:
  - Heart failure hospitalization
  - All-cause death

Control outcomes of interest (control outcomes only serve to assess aspects of study validity but are not further interpreted, definitions provided in Appendix A):

1. Bleeding (we expect to see a null association, as renin angiotensin aldosterone inhibitors are not expected to have any impact on this outcome)

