## 9. Balance Assessment

Optum- <https://bwh-dope.aetion.com/projects/details/1069/results/63131/result/0>

MarketScan- <https://bwh-dope.aetion.com/projects/details/1072/results/63129/result/0>

Medicare- <https://bwh-dope.aetion.com/projects/details/1073/results/63128/result/0>

Date conducted: 12/22/2020

After review of initial feasibility and power analyses, complete creation of the remaining covariates from Section 6.2. Again, using the

dummy outcome of a 90-day gap in database enrollment, complete a 1:1 PS-matched analysis. The PS should include the complete list of covariates.

- Provide plot of PS distributions stratified by treatment group.

Note- Please refer to **Appendix B**.

- Report covariate balance after matching.

Note- For Table 1, please refer to **Appendix B**.

- Report reasons for censoring by treatment group.

	Overall	Referent	Exposure
Dummy outcome	0 (0%)	0 (0%)	0 (0%)
Death	150 (2.47%)	64 (2.11%)	86 (2.84%)
Start of an additional exposure	309 (5.09%)	106 (3.49%)	203 (6.69%)
End of Index Exposure	2285 (37.67%)	1206 (39.76%)	1079 (35.58%)
Specified date reached	1868 (30.79)	879 (28.98%)	989 (32.61%)
End of patient enrollment	696 (11.47%)	366 (12.07%)	330 (10.88%)
Switch to ARBs or Aliskiren + Nursing Home admission Occurred	758 (12.50%)	412 (13.58%)	346 (11.41%)

- Report follow-up time by treatment group.

Patient Group	Optum Median Follow-Up Time (Days) [IQR]	MarketScan Median Follow-Up Time (Days) [IQR]	Medicare Median Follow-Up Time (Days) [IQR]
Overall Patient Population	118 [58, 286]	139 [59, 296]	102 [46, 189]
Referent - ACE Inhibitors	126 [60, 309]	142 [77, 295]	102 [42, 170]
Exposure - Sacubitril/Valsartan	108 [56, 266]	136 [58, 300]	106 [58, 218]

- Report overall risk of the primary outcome.

	Optum	MarketScan	Medicare	Pooled
Risk per 1,000 patients	206.6	160.3	248.0	215.3

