# Appendix B: Sacubitril/Valsartan vs. ACE Inhibitors

Other Medication - DPP-4 Inhibitors ; n (%)	90 (7.0%)	85 (6.6%)	0.0159	56 (7.5%)	46 (6.1%)	0.0556	90 (8.9%)	85 (8.4%)	0.0178	180 (5.9%)	170 (5.6%)	0.0129
Other Medication - GLP-1 RA ; n (%)	51 (4.0%)	51 (4.0%)	0.0000	21 (2.8%)	23 (3.1%)	-0.0177	17 (1.7%)	13 (1.3%)	0.0329	068 (2.2%)	064 (2.1%)	0.0069
Other Medication - Metformin ; n (%)	337 (26.3%)	341 (26.7%)	-0.0091	179 (23.9%)	172 (23.0%)	0.0212	218 (21.7%)	217 (21.0%)	0.0024	555 (18.3%)	558 (18.4%)	-0.0206
Other Medication - NSAIDS (COX-2 Selective) ; n (%)	72 (5.6%)	64 (5.0%)	0.0268	36 (4.8%)	31 (4.1%)	0.0340	43 (4.3%)	43 (4.3%)	0.0000	115 (3.8%)	107 (3.5%)	0.0160
Other Medication - NSAIDS (Non-Selective) ; n (%)	126 (9.9%)	129 (10.1%)	-0.0067	136 (18.2%)	137 (18.3%)	-0.0026	35 (3.5%)	34 (3.4%)	0.0055	161 (5.3%)	163 (5.4%)	-0.0044
Other Medication - Use of antiplatelet agents ; n (%)	355 (27.8%)	377 (29.5%)	-0.0276	249 (32.2%)	237 (31.7%)	0.0242	282 (38.0%)	292 (39.0%)	-0.0232	637 (21.0%)	669 (22.1%)	-0.0268
Other Medication - Use of heparin and other low-molecular weight heparins ; n (%)*	29 (2.3%)	27 (2.1%)	0.0136	1 (0.1%)	0 (0.0%)	0.0447	27 (3.7%)	9 (0.9%)	0.1357	056 (1.8%)	036 (1.2%)	0.0494
Other Medication - Use of oral anti-coagulants ; n (%)	478 (37.4%)	470 (36.7%)	0.0145	255 (34.1%)	270 (36.1%)	-0.0419	429 (42.6%)	419 (41.7%)	0.0182	907 (29.9%)	889 (29.3%)	0.0131
Other Medication - Use of other hypertension drugs ; n (%)	149 (11.6%)	140 (10.9%)	0.0222	105 (14.0%)	97 (13.0%)	0.0293	105 (10.4%)	108 (10.7%)	-0.0098	254 (8.4%)	248 (8.2%)	0.0072
Other Medication - Use of antipsychotics ; n (%)	33 (2.6%)	36 (2.8%)	-0.0123	10 (1.3%)	11 (1.5%)	-0.0170	32 (3.2%)	27 (2.7%)	0.0296	065 (2.1%)	063 (2.1%)	0.0000
Other Medication - Use of dementia meds ; n (%)	35 (2.7%)	25 (2.0%)	0.0462	15 (2.0%)	14 (1.9%)	0.0072	33 (3.3%)	34 (3.4%)	-0.0056	068 (2.2%)	059 (1.9%)	0.0212
Other Medication - Use of antiparkinsonian meds ; n (%)	34 (2.7%)	38 (3.0%)	-0.0180	13 (1.7%)	13 (1.7%)	0.0000	26 (2.6%)	29 (2.9%)	-0.0183	060 (1.9%)	060 (1.9%)	-0.0139
Other Medication - Use of anxiolytics/hypnotics ; n (%)	78 (6.1%)	81 (6.3%)	-0.0093	39 (6.2%)	54 (7.2%)	-0.0830	54 (5.4%)	60 (6.2%)	0.0342	132 (4.6%)	143 (4.7%)	-0.0144
Other Medication - Use of anticoagulants ; n (%)	181 (14.2%)	194 (15.2%)	-0.0282	76 (10.2%)	68 (9.1%)	0.0373	165 (16.5%)	165 (16.4%)	0.0027	347 (11.4%)	359 (11.6%)	-0.0125

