...median (IQR)	15.93 [5.74, 32.88]	18.14 [6.52, 33.73]	-0.0600	10.53 [3.58, 20.38]	12.40 [5.11, 19.94]	-0.1150	16.10 [5.26, 32.03]	18.78 [5.57, 34.95]	-0.0796	14.65 (36.11)	16.94 (26.88)	-0.0719
SES Proxy - Low income indicator; n (%)	275 (21.5%)	299 (23.4%)	-0.0455	0 (0.0%)	0 (0.0%)	#DIV/0!	0 (0.0%)	0 (0.0%)	#DIV/0!	275 (9.1%)	299 (9.9%)	-0.0273
SES Proxy - Business type												
...Commercial; n (%)	325 (25.4%)	340 (26.6%)	-0.0274	0 (0.0%)	0 (0.0%)	#DIV/0!	0 (0.0%)	0 (0.0%)	#DIV/0!	325 (10.7%)	340 (11.2%)	-0.0160
...Medicare; n (%)	954 (74.6%)	939 (73.4%)	0.0274	0 (0.0%)	0 (0.0%)	#DIV/0!	0 (0.0%)	0 (0.0%)	#DIV/0!	954 (31.5%)	939 (31.0%)	0.0108
SES Proxy - Insurance Plan type												
...Comprehensive; n (%)	0 (0.0%)	0 (0.0%)	#DIV/0!	105 (14.0%)	94 (12.6%)	0.0412	0 (0.0%)	0 (0.0%)	#DIV/0!	105 (3.5%)	094 (3.1%)	0.0224
...HMO; n (%)	0 (0.0%)	0 (0.0%)	#DIV/0!	62 (8.3%)	71 (9.5%)	-0.0422	0 (0.0%)	0 (0.0%)	#DIV/0!	062 (2.0%)	071 (2.3%)	-0.0207
...PPD; n (%)	0 (0.0%)	0 (0.0%)	#DIV/0!	403 (53.9%)	400 (53.5%)	0.0080	0 (0.0%)	0 (0.0%)	#DIV/0!	403 (13.3%)	400 (13.2%)	0.0029
...Others; n (%)	0 (0.0%)	0 (0.0%)	#DIV/0!	178 (23.8%)	183 (24.5%)	-0.0164	0 (0.0%)	0 (0.0%)	#DIV/0!	178 (5.9%)	183 (6.0%)	-0.0042
SES Proxy - Dual status code (with Medicaid); n (%)	0 (0.0%)	0 (0.0%)	#DIV/0!	0 (0.0%)	0 (0.0%)	#DIV/0!	202 (20.1%)	203 (20.2%)	-0.0025	202 (6.7%)	203 (6.7%)	0.0000

\*Excluded from P5 model: Age Categories, Use of Lithium, Use of AGI & Meglitinides, PCSK9 Inhibitors, Use of heparin or LMWH, Hemodialysis/Peritoneal dialysis

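### Heparin/LMWH use is left out of the propensity score without a reason and stays imbalanced in matched Medicare patients, which slightly shifts the null expected for bleeding, the only control outcome

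*Protocol*

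**What the plan says.** On the content of the PS, Section 9 (Balance Assessment) states: "The PS should include the complete list of covariates". The footnote under the matched table in Appendix B then lists what was dropped: "Excluded from P5 model: Age Categories, Use of Lithium, Use of AGI & Meglitinides, PCSK9 Inhibitors, Use of heparin or LMWH, Hemodialysis/Peritoneal dialysis". No reason is printed for any of the six items.

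The matched table gives heparin/LMWH use (ACE inhibitors, then sacubitril/valsartan, then standardized difference) as:

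- Optum: "29 (2.3%) 27 (2.1%) 0.0136"
- MarketScan: "1 (0.1%) 0 (0.0%) 0.0447"
- Medicare: "27 (3.7%) 9 (0.9%) 0.1357"
- Pooled: "056 (1.8%) 036 (1.2%) 0.0494"

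Section 6.3.1 names one control outcome: "Bleeding (we expect to see a null association, as renin angiotensin aldosterone inhibitors are not expected to have any impact on this outcome". On the role of such outcomes it says: "control outcomes only serve to assess aspects of study validity but are not further interpreted".

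**The concern.** The footnote departs from the protocol's own rule for the PS, and for this covariate the reason is not obvious. Age categories duplicate continuous age, which is not on the excluded list. Lithium and PCSK9 inhibitors have 0 to 3 users in each matched arm. Heparin/LMWH has 29 and 27 matched users in Optum and 27 and 9 in Medicare. A rarer covariate, SGLT-2 inhibitors in Medicare (2 vs 5), carries no exclusion mark.

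The choice of covariate matters because of the control outcome. The argument for a null bleeding result is that the drug class should not affect bleeding. A measured, bleeding-related difference between the arms gives a second reason for a non-null result. It acts in a known direction: fewer heparin/LMWH users on sacubitril/valsartan pulls the bleeding hazard ratio below 1. At stake is how cleanly the one listed diagnostic can be read, chiefly in Medicare.

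**Working it through.** **Inputs.** Counts and arm sizes come from the Appendix B tables. Matched arms are 1,279 (Optum), 748 (MarketScan), 1,006 (Medicare) and 3,033 (pooled). Medicare before matching is 472 of 18,303 vs 18 of 1,658. The effect of heparin/LMWH on bleeding is not in the protocol; relative risks (RR) of 2, 3 and 5 are assumed.

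**Step 1: reproduce the printed standardized differences.** With p0 for ACE inhibitors and p1 for sacubitril/valsartan, d = (p0 − p1) / √{[p0(1 − p0) + p1(1 − p1)] / 2}.

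- Medicare matched: 27/1,006 = 2.7% and 9/1,006 = 0.9%, so d = 0.018 / √[(0.027 × 0.973 + 0.009 × 0.991)/2] = 0.018/0.1326 = 0.1357, as printed.
- Medicare before matching: 2.6% vs 1.1%, d = 0.015/0.1345 = 0.1115, as printed.
- Optum matched: 2.3% vs 2.1%, d = 0.002/0.1467 = 0.0136, as printed.
- Pooled matched: 1.8% vs 1.2%, d = 0.006/0.1215 = 0.0494, as printed.

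The percentage printed beside the Medicare count of 27 does not equal 27/1,006. Neighbouring cells show the same kind of leading-digit slip, which text extraction can produce. I use the counts and make nothing of it.

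**Step 2: place the imbalance.** Matching without the term did not reduce the Medicare difference (0.1115 before, 0.1357 after). It is the largest among the legible matched Medicare rows; the next are median age (−0.1335) and median number of distinct prescriptions (−0.1128). Some rows are cut off, so this ranking covers legible rows only. In absolute terms the gap is 27 − 9 = 18 patients, or 1.8 percentage points.

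**Step 3: size the effect on the bleeding null.** With no true drug effect, and no other imbalance, the expected ratio is [1 + p1(RR − 1)] / [1 + p0(RR − 1)]. For the pooled line I sum the databases: 29 + 1 + 27 = 57 vs 27 + 0 + 9 = 36. The printed pooled 56 leaves out the one MarketScan user.

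| Assumed RR | Medicare (27 vs 9 of 1,006) | Pooled (57 vs 36 of 3,033) |
|---|---|---|
| 2 | 1.0089/1.0268 = 0.983 | 1.0119/1.0188 = 0.993 |
| 3 | 1.0179/1.0537 = 0.966 | 1.0237/1.0376 = 0.987 |
| 5 | 1.0358/1.1074 = 0.935 | 1.0475/1.0752 = 0.974 |

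**Step 4: could the test see it?** Events needed for 80% power at two-sided 0.05 with equal arms are 4(1.96 + 0.84)² / (ln HR)², or about 31.4/(ln HR)². For 0.935 this is 31.4/0.00452, about 6,950 bleeding events. Medicare has 2 × 1,006 = 2,012 matched patients, and all three databases together have 6,066.

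**The case against.** A reader might infer that the control test is confounded and cannot serve its purpose. The documents do not support that:

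- The shift is a few percent under the assumed range, and Step 4 shows that the test could not detect it.
- A difference above 0.1 occurs in one database only.
- The main antithrombotic exposures are balanced in matched Medicare: oral anticoagulants 429 vs 419 (0.0182) and antiplatelet agents 282 vs 292 (−0.0232).
- The row records baseline use, and nothing shows that it continued into follow-up, so even the assumed relative risks may be generous.
- Section 6.3.1 gives control outcomes a limited role.
- A negative control exists to reveal residual imbalance, so a non-null result caused by heparin/LMWH would be a true signal of incomplete matching.

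All of this stands as to size. The last argument is weaker for a covariate that is already measured: a control outcome is more useful when known differences have been removed and it can speak to unknown ones. The exclusion is also openly disclosed, by asterisk and footnote. But disclosure is not a reason, and the conflict with Section 9 remains.

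**Conclusion.** The point holds as a minor one. The PS omits heparin/LMWH against the rule in Section 9, without a stated reason, and sparsity accounts for this only in MarketScan. The consequence is confined to Medicare, with a standardized difference of 0.136. If the bleeding relative risk is 2 to 5, the expected null there moves to about 0.98 to 0.94, and to about 0.99 to 0.97 pooled, towards fewer bleeds on sacubitril/valsartan. These figures rest on the assumed relative risk and on baseline use standing in for exposure during follow-up.

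This does not make the control test invalid, and it is not evidence of bias in the primary result. Nor can the point be extended to the other items in the footnote: age categories are redundant, lithium and PCSK9 inhibitors are sparse, and the remaining two have no legible row from which to judge.

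**What to change.** State in Appendix B why heparin/LMWH was excluded, and do one of the following in Medicare:

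- **Re-match.** Add heparin/LMWH to the Medicare PS model and repeat the match before outcomes are analysed. The covariate is already collected, and balance was assessed on a dummy outcome, so this can be done without sight of results. The cost is that matched pairs may change, so Medicare and pooled balance and power would have to be reported again.
- **Keep the match.** Adjust the Medicare bleeding model for baseline heparin/LMWH use and say so in advance. This leaves the primary-outcome cohort and the final power assessment untouched. It handles the control outcome only, and the footnote would still depart from Section 9, so the stated reason is needed all the more.

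No change is needed in Optum, which is balanced at 0.014 without the term, or in MarketScan, which has a single user.
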